1 INTRODUCTION

1.1 Background and Rationale

Amyotrophic lateral sclerosis (ALS) is a progressive and fatal neurodegenerative disease that affects motor neurons in the spinal cord, brainstem and motor cortex. Clinical features include fasciculations, muscle wasting and weakness, spasticity, and hyper- or hyporeflexia. Respiratory complications usually develop in patients with advanced disease, and the cause of death is generally the paralysis of the respiratory muscles and diaphragm (Beghi et al., 2007). Although the exact pathophysiological mechanisms underlying neurodegeneration in ALS remain uncertain, a common pathological hallmark is the presence of ubiquitin-immunoreactive cytoplasmic inclusions in degenerating neurons, followed by an inflammatory reaction (McGeer and McGeer, 2002; Bendotti et al. 2012; Malaspina et al., 2015). Prominent neuroinflammation can be observed in pathologically affected areas of the central nervous system (CNS) and in spinal cords from both human ALS patients and mouse models of the disease (McGeer and McGeer, 2002; Philips and Robberecht, 2011). Typically, inflammation in ALS is characterized by gliosis and the accumulation of large numbers of activated microglia and astrocytes. Activation of glia is marked by elevated production of potentially cytotoxic molecules such as ROS, inflammatory mediators such as COX-2, and proinflammatory cytokines such as IL-1 β , TNF- α , and IL-6 (McGeer and McGeer, 2002). Major histocompatibility complex molecules and complement receptors are highly expressed by reactive microglia in the primary motor cortex and in the anterior horn of the spinal cords of ALS patients (McGeer and McGeer, 2002; Sta et al., 2011). The major determinants of motor neuron death in ALS remain to be established.

A motor neuron-specific death pathway has been suggested for ALS based on the finding that motor neurons isolated from transgenic superoxide dismutase 1 (SOD1) mutant mice were more sensitive to Fas- or nitric oxide (NO)-triggered cell death than wild-type motor neurons (Raoul et al., 2002). Upon binding of FasL to the Fas receptor, the intracellular portion of Fas recruits the adaptor molecule FADD (Fas Associated Death Domain), which then activates a caspase cascade that culminates in the death of motor neurons. This pathway was also activated in presymptomatic ALS mice (Raoul et al., 2006). Given that astrocytes and microglia produce NO and that astrocytes from SOD1 mutant mice produce FasL (Barbeito et al., 2004), glial cells could directly kill motor neurons. Another member of the same receptor family, the p75 neurotrophin receptor, has also been implicated in ALS-dependent motor neuron death (Pehar et al., 2004). Specifically, nerve growth factor secreted by SOD1 mutant astrocytes induced the death of motor neurons expressing p75 by a mechanism involving the formation of NO and peroxinitrite (Pehar et al., 2004). Peroxynitrite

converts tyrosine to 3-nitrotyrosine (3-NT), leading to protein nitration. Interestingly, high levels of nitrated proteins were found in the spinal cord and peripheral blood mononuclear cells (PBMC) of mutant SOD1 animal models, already at a presymptomatic stage of the disease, and in PBMC of sporadic ALS patients (Casoni et al., 2005; Nardo et al., 2009; Nardo et al., 2011).

Even though motor neurons are the main cells affected in ALS, increasing evidence points to the involvement of neighboring glia cells during pathogenesis (Clement et al., 2003; Yamanaka et al., 2008a). Cell-specific deletion of mutant SOD1 in astrocytes and microglia reduced disease severity and boosted the survival of ALS mice (Boilley et al., 2006; Yamanaka et al., 2008a). Evidence for a role for non-neuronal cells has been obtained using chimeric mice selectively expressing SOD1 in neurons or in non-neuronal cells (Yamanaka et al., 2008b). In chimeric mice expressing high levels of mutant SOD1 in 100% of motor neurons and oligodendrocytes, the presence of wildtype neighboring support cells substantially delayed the onset of motor neuron degeneration. Gene expression profiling implies that inflammatory cascades are activated before the initiation of motor neuron degeneration, suggesting that inflammation could be involved in the presymptomatic phase of the disease (Vargas et al., 2008). Mutant SOD1, but not the wild-type protein, has been proposed to be secreted into the extracellular space via chromogranin vesicles, causing activation of microglia and resulting in motor neuron death in culture (Urushitani et al., 2006). Consistently, mutant SOD1 is present in the cerebrospinal fluid of ALS patients and is toxic to rodent spinal cord cultures (Tikka et al., 2002). Moreover, intracerebral infusion of mutant SOD1 into wild-type mice induced microglial activation and cytokine production (Kang and Rivest, 2007).

Emerging evidence points to an involvement of the adaptive immune response in ALS disease progression. In fact, increased levels of CD4+ and CD8+ T lymphocytes and dendritic cells were detected in close proximity to dying motor neurons in the spinal cords of SOD1 mutant mice (Chiu et al., 2008) and in the brain parenchyma of ALS patients (Kawamata et al., 1992; Henkel et al., 2004). Infiltrating T cells (Th2, Treg) can be neuroprotective after secreting IL-4, which signals reactive microglia to produce neurotrophic factors such as insulin growth factor (IGF-1) (Chiu et al., 2008). In the case of ALS, as in Alzheimer's disease (AD) and Parkinson's disease (PD) as well as other neurodegenerative diseases in which microglia and astrocytes are the primary contributors to inflammation, therapeutic approaches logically would aim to modulate the sensor/transducer/effectector functions of the innate immune system, that is, TLRs, NF- κ B, and TNF- α , respectively. These findings suggest that targeting inflammatory pathways might be effective in preventing disease progression.

The only drug showing to improve survival in patients with ALS is riluzole (Miller et al, 2007). However, the benefits consist in a three-month delay of death while disability and other outcome measures are virtually unaffected. This highlights the need to test novel approaches to slow the progression of the disease.

1.2 Pre-clinical Data

RNS60 is a novel, anti-inflammatory and cytoprotective drug that has shown remarkable efficacy in animal models of neuroinflammation and neurodegeneration. In multiple *in vitro* and *in vivo* models of different inflammatory diseases, treatment with RNS60 has shown favorable effects ranging from reduced levels of pro-inflammatory cytokines to improved functional outcomes. With direct relevance for this study, intraperitoneal and intravenous (IV) injections of RNS60 in multiple rodent EAE models showed a remarkable improvement of clinical scores, reduction in the expression of inflammatory molecules such as IL-17 and iNOS, reduced gliosis and CNS infiltration by inflammatory cells, and finally reduced demyelination. Moreover, intraperitoneal injection of RNS60 caused significant down regulation of proinflammatory molecules in the brain, and neuronal protection in mouse models of AD and PD. RNS60 inhibited microglial inflammation via type 1A phosphatidylinositol-3 kinase-Akt-CREB-mediated upregulation of $I\kappa B\alpha$ and inhibition of NF- κB activation in cultured glial cells (Khasnavis, S. et al, 2012). Similarly, RNS60 suppressed NF- κB activation through differential modulation of type 1A PI(3)K pathways in a mouse model of PD, and thereby protected mice against neurodegeneration (Khasnavis S et al, 2014). In a rodent EAE model, RNS60 treatment achieved a remarkable improvement of clinical scores, reduction in the expression of inflammatory molecules such as IL-17 and iNOS, reduced CNS infiltration by inflammatory cells, and finally reduced demyelination (Mondal, S. et al. 2012).

In both, *in vitro* and *in vivo* models of familial ALS carrying SOD1G93A mutation, we recently observed a reduced up-regulation of iNOS induced by lipopolysaccharide (LPS) in astrocytes (Fig 1.A) and a protective effect of RNS60 on motor neurons. In an *in vitro* model of ALS, consisting of co-cultures of astrocytes and spinal neurons expressing human SOD1 with G93A mutation, RNS60 led to a reduced spontaneous and selective loss of large mutant motor neurons (Fig 1.B). *In vivo*, the intraperitoneal treatment of SOD1G93A mice with RNS60 at the onset of the disease (evaluated at their body weight peak) caused a significant delay in the appearance of motor dysfunction (Fig.1C) and a partial but significant preservation of lumbar spinal cord motor neurons (Fig 1.D) and neuromuscular junctions (Fig 1.E). Moreover, RNS60 treatment led to a small but significant activation of the neuroprotective PI3K-Akt signaling pathway, as demonstrated by the increased phosphorylation of Akt in lumbar spinal cord (Fig 1.F). This demonstrates that the same pathways are modulated by RNS60 across preclinical models of different neurodegenerative diseases.

[figure not shown]

Figure 1. Effect of RNS60 in SOD1^{G93A} linked ALS models *in vitro* and *in vivo*. **A) RNS60 reduces LPS-induced iNOS in astrocytes cultures.** The iNOS mRNA is normalized to SOD2 mRNA levels. Data are mean \pm SEM (n=4 independent experiments) and analyzed by One Way ANOVA (p value<0.001), Tukey Test: ***p<0.001 and **p<0.01 vs. untreated, \$\$\$p<0.005 vs. LPS and \$p<0.05 vs. LPS+RNS60. **B) RNS60 protects motor neurons in astrocyte-spinal neuron co-cultures from SOD1^{G93A} mice.** Data are mean \pm SEM (n=5 independent experiments) and analyzed using Two Way ANOVA (int. p <0.04), Tukey Test: **p<0.01 vs. NTG untreated, \$p<0.05 vs. SOD1^{G93A} untreated and \$\$p<0.01 vs. NTG NS. **C) RNS60 treatment delays the onset of neuromuscular symptoms in SOD1^{G93A} mice.** The age of onset is considered as the age at which the mouse fails the grip strength test for the first time (grip latency <90 sec). The curves are evaluated by the Log-rank (Mantel-Cox) test (Chi square= 17.10, p <0.001). **D) RNS60 treatment protects motor neurons in SOD1^{G93A} mice.** Motor neuron count from spinal cord L2-L5 segment (10 sections/mouse). The bar graph represents mean \pm SEM (n=3 mice per group). Data are analyzed using t-test (p<0.0001). **E) RNS60 slightly protects neuromuscular junctions from denervation.** Data represent denervated plaques as the percentage of total plaques counted in ten frames per section, five sections for each mouse, at 20X-magnification (n=5). At symptomatic stage, SOD1^{G93A} mice treated with NS show significant denervation (61.76%), which is slightly reduced by the treatment with RNS60 (52.35%). Histograms show the mean \pm SEM of 5 mice per group. Data are analyzed using t-test (p=0.0237). **F) RNS60 activates PI3K-Akt signaling in the lumbar spinal cord.** Western blot of lumbar spinal cord proteins show that the level of phosphorylated Akt (p-Akt) is higher in SOD1^{G93A} mice treated with RNS60 as compared to NS-treated controls. The bar graph represents mean \pm SEM (n=5 mice per group). Data are analyzed using t-test (p=0.05).

Therefore, RNS60 presents itself as a promising candidate for the treatment of ALS. Its exceptional safety profile, demonstrated both in preclinical toxicology studies and Food and Drug Administration (FDA)-approved clinical phase I studies upon inhaled and IV administration, supports testing of RNS60 in clinical phase II studies in ALS patients.

1.3 Pre-clinical Toxicology Data

Extensive *in vitro* and *in vivo* preclinical testing of RNS60 has been completed at multiple institutions and in various models. RNS60 did not show any concerning signs of toxicity in any of the *in vitro* cell culture studies performed to date or in the animal toxicology studies conducted in accordance with FDA guidelines for Investigational New Drug (IND) Applications. The administration of the maximum deliverable dose of RNS60 by bolus injections (10 mL/kg) or IV infusion for 6 (48 mL/kg) or 24 hours (96 mL/kg) daily for 28 days was well tolerated in albino rats. There were no RNS60-related mortalities, clinical observations, ocular observations, abnormal laboratory results (serum chemistry, hematology and urinalysis), organ weight changes, macroscopic or microscopic observations or genotoxic activity. The administration of the maximum deliverable dose of RNS60 by bolus injections (10 mL/kg) or IV infusion for 6 (48 mL/kg) or 24 hours (96 mL/kg) once daily for 28 days was well tolerated and did not reveal toxicity in any target organs in cynomolgus monkeys.

In the bacterial reverse mutation assay (Ames assay) using *Salmonella typhimurium* strains (TA98, TA 100, TA 1535 and TA 1537) and *Escherichia coli* WP uvrA in the presence and absence of S9 metabolic activation, RNS60 caused neither an increase in the number of revertant colonies nor a dose-related response in any of the tested strains at any dose level. In the mouse lymphocyte assay, RNS60 similarly demonstrated minimal cytotoxicity and did not increase the mutation frequency relative to the vehicle controls in either the presence or absence of metabolic activation. Therefore, it was concluded that RNS60 was not mutagenic.

1.4 Clinical Data to Date

RNS60 has been well tolerated in human safety studies, both after IV infusion and when administered by inhalation. In a Phase I safety and tolerability study (Clinicaltrials.gov # NCT01264783), RNS60 was administered to 9 healthy subjects as continuous IV infusion at 3 subsequently increasing rates of 100 mL/h, 150 mL/h, and 200 mL/h over 48 hours at each rate. No serious adverse events (SAEs) were reported in this study and no subjects were discontinued from the study due to an adverse event (AE). Furthermore, no clinically relevant changes were noted in clinical laboratory tests, vital signs, physical examinations, oral fluid intake or urine output. The most frequently reported AE was mild headache, which occurred most often in the highest infusion

rate of 200 mL/h, and was considered possibly related to the treatment. However, there was an increase in overall incidence with the increased infusion rate for both placebo and RNS60-treated subjects, with 55% of subjects in the RNS60 group and 33% of subjects in the placebo group reporting mild headache. Since headache is a common symptom of fluid (volume) load it is probable that the headaches were primarily a volume-related effect of the infusion. Other AEs reported as treatment related were a single incidence each (11.1%) of mild arthralgia, mild limb discomfort, and moderate musculoskeletal pain. Cardiac monitoring showed only mild, sporadic and infrequent Electrocardiogram (EKG) changes from baseline; however these changes were not attributed to use of RNS60.

In a second Phase I study (Clinicaltrials.gov # NCT01057498), RNS60 administered to 16 subjects with mild to moderate asthma by inhalation through a nebulizer, at a 4-mL dose twice a day for 28 days was well tolerated. No SAEs were reported in this study and no subjects were discontinued from the study due to an AE. Furthermore, no clinically relevant changes were noted in clinical laboratory tests, vital signs, or physical examinations. The most commonly reported treatment related AE was mild oropharyngeal pain, reported by 2 subjects (12.5%). One subject (6.3%) reported a single incidence of moderate nasal mucosal disorder. Other AEs reported as treatment related were all mild, and were single incidences (6.3%) of eye allergy, ocular hyperemia, chest discomfort, increased blood pressure, increased appetite, headache, somnolence, allergic sinusitis, cough, dyspnea, nasal congestion, throat irritation, and pruritus. Additionally, RNS60 treatment did not cause bronchoconstriction, but rather demonstrated positive effects on forced expiratory volume in 1 second (FEV₁) and peak expiratory flow measurements, as well as improved quality of life scores.

In a third Phase I study (Clinicaltrials.gov # NCT01511302), RNS60 administered by nebulization in combination with a budesonide (BD) dose of either 0.25 mg or 0.5 mg for 28 days, to subjects with mild to moderate asthma who were previously taking a prescribed corticosteroid, was also well tolerated. 57 subjects were treated with the combination of RNS60 and BD (RNS60-BD). No SAEs were reported and no discontinuation of subjects occurred that were related to use of RNS60-BD. AEs attributed to the use of RNS60-BD were sporadic, with single incidences (3.4%) of moderate migraine, moderate wheezing, moderate asthma prophylaxis, mild chest discomfort, and mild increase in hepatic enzymes. Furthermore, there were no significant findings noted in clinical laboratory tests, vital signs, or physical examinations. Additionally, use of RNS60-BD did not cause any incidence of clinically significant bronchoconstriction; rather it demonstrated positive

trends in quality of life improvements and reduced use of rescue inhalers. For details of these studies refer to the Investigator's Brochure (IB) for RNS60.

An ongoing interventional Phase II trial with a weekly IV infusion of RNS60 in relapsing/remitting multiple sclerosis (RRMS) patients is currently enrolling subjects at the University hospitals in Zurich and Innsbruck.

An ongoing single center, open label, pilot trial of RNS60 in ALS patients is enrolling at Massachusetts General Hospital. Subjects are receiving weekly IV infusion of RNS60 in addition to daily inhalation of RNS60 for six months while being monitored for disease progression and microglial activation by PET imaging.

1.5 Description of RNS60

Chemically, RNS60 consists of 0.9% sodium chloride and dissolved oxygen. RNS60 is manufactured by electrokinetic processing in Revalesio's patented Revalesio Pump (RP). During operation of the RP, the fluid is exposed to very strong hydrodynamic, rotational, vortical and longitudinal shear forces, resulting in forceful dispersion of the oxygen. The combined effect of these forces alters the physical relationship between gas and liquid, and has a concomitant effect on the electrical properties of the fluid caused by a reorganization of ionic charges and the formation of associated electrical double layers. RNS60 does not contain a chemical Active Pharmaceutical Ingredient (API).

The observed bioactivity of RNS60 is, instead, based on the presence of charge-stabilized nanostructures (CSN) generated by the electrokinetic processing in the RP. The CSNs consist of an oxygen core surrounded by layers of separated positive and negative electrical charges. The electrical charges associated with the core oxygen stabilize the layers of separated electrical charges and form CSN-associated electrical fields in RNS60.

1.6 Tolerability

As stated in the previous sections referring to preclinical toxicology work, minimal adverse effects were seen with the treatment of RNS60. Section 1.4 explains how RNS60 was safe and well tolerated in multiple human safety studies. RNS60 has demonstrated safety when administered to subjects via inhalation as well as when administered intravenously.

1.7 Dose Rationale

The IV and inhaled doses of RNS60 have been selected based on previous experience in clinical studies. Because no safety concerns have been identified to date, these doses are expected to be well

tolerated by the subjects and provide appropriate exposure to test the hypothesis of the study. The importance of remaining within the margin of safety in dose selection has been taken into account while maximizing dosing frequency without infringing on practicality for subjects.

1.8 Pharmacokinetics

The observed bioactivity of RNS60 is not based on an API, as RNS60 contains neither a chemical drug substance nor a biologic. Instead, the bioactivity is caused by a physical property of RNS60 that is associated with the presence of CSNs generated by the electrokinetic processing in the RP. The CSNs consist of an oxygen core surrounded by layers of separated positive and negative electrical charges. Preclinical studies have conclusively demonstrated that the oxygen alone is not responsible for RNS60's bioactivity, but that it is the combination of oxygen with the processing in the RP that results in a physical quality of the fluid that is able to modulate the stress response of cells. As it is currently impossible to directly image CSNs *in vivo*, traditional pharmacokinetic evaluations are not applicable to RNS60. Preclinical data clearly demonstrate, however, that RNS60 is able to modulate the type 1A PI(3)K signaling pathway within the CNS after systemic administration. RNS60 induced the activation of type IA phosphatidylinositol-3 kinase (PI3K) in the substantia nigra of healthy as well as MPTP-intoxicated mice within 3 hours post intraperitoneal injection, and the effect was sustained until 6 hours post injection (Khasnavis S *et al.* 2014). Thus, RNS60 is expected to mediate its effects both on peripheral immune cells as well on CNS targets, as reported earlier (Modi, KK. *et al.* 2014; Khasnavis, S. *et al.* 2014; Mondal, S. *et al.* 2012).

2 STUDY OBJECTIVES AND OUTCOMES

2.1 Primary Objective

To measure the effect of RNS60 treatment on selected pharmacodynamic biomarkers in ALS patients concurrently treated with riluzole. Candidate markers include:

1. T-reg (measured via FOXP3 and CD25 mRNA);
2. Cyp-A;
3. 3-NT;
4. Actin-NT;
5. MCP-1;
6. IL-17.

2.2 Secondary Objectives

1. The preliminary efficacy of RNS60 on functional disability, as measured by the ALSFRS-R scale;
2. The preliminary efficacy of RNS60 in prolonging survival (or time to tracheostomy, whichever comes first);
3. The preliminary efficacy of RNS60 in slowing the decline of forced vital capacity (FVC) from baseline;
4. The tolerability and safety of RNS60 through the identification of unexpected adverse events;
5. The impact of RNS60 on quality of life as measured by ALSAQ-40 scale.

2.3 Primary Endpoint

The mean change over time in the proportion of T-reg (measured via FOXP3 and CD25 mRNA); the mean change over time in the plasma concentrations of Cyp-A, 3-NT, Actin-NT, MCP-1, IL-17 in the two treatment arms, during the entire treatment period (from baseline to 24 weeks).

2.4 Secondary Endpoints

1. The mean change in the proportion of T-reg (measured via FOXP3 and CD25 mRNA); the mean change over time in the plasma concentrations of Cyp-A, 3-NT, Actin-NT, MCP-1, IL-17 during the follow up period (from 24 to 48 weeks);
2. The cumulative proportion of subjects becoming no longer self-sufficient at 4, 12, 24, 36 and 48 weeks in the two treatment arms (defined as those scoring 2 or lower on at least one of the ALSFRS-R items for swallowing, cutting food and handling utensils, or walking);
3. The mean change of ALSFRS-R total score in the two treatment arms during the treatment and follow up period;
4. The cumulative proportion of deaths or tracheostomies in the two treatment arms during the entire study including follow-up;
5. The mean change of FVC score in the two treatment arms during the treatment and follow up period;
6. The total number of subjects in the two treatment arms experiencing at least one AE leading to treatment discontinuation at 4, 12 and 24 weeks;
7. The mean number of AEs per treatment arm at 4, 12, 24 and 48 weeks;

8. The mean change of ALSAQ-40 score measuring quality of life at the completion of the treatment and follow up period.

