6.12 Modification of Study Intervention/Investigational Product for a Subject

Any dosage adjustment, including the reason for and dates of adjustment, will be documented in the CRF for each subject requiring this manipulation. The PIs or licensed physician Sub-Investigator may reduce the dosage of study drug or discontinue the study drug in its entirety for AEs thought to be related to the study drug or for other reason during the trial (the reason for, and dates of

suspension or dose reduction must be documented). If the AE is mild or moderate, the dosage may be reduced until the event improves. The PIs may then choose to resume the higher dosage or maintain the subject at a reduced dosage. The option to continue with administration by IV only or inhalation only is allowable.

If the event is serious or life threatening, and deemed to be definitely drug related, the study drug will be discontinued immediately. Study subjects must remain off the study drug permanently. Subjects may not resume study drug. All AEs will be followed to resolution.

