The numerical change of FVC, ALSFRS-R and ALSAQ-40 during the treatment and follow-up period will be assessed using repeated measures ANOVA, with an unspecified variance covariance matrix. The hypothesis will be tested using the time*treatment interaction which measures differences in the slope of the ALSFRS-R. Survival (time to death or tracheostomy) and time to functional disability (i.e., to reach a non self-supporting status or death or tracheostomy) will be assessed using actuarial methods with death and non-self supporting status as end-points. Survival will be described with the Kaplan-Meier method. Differences between the two treatment groups will be compared using the log-rank test. The statistical significance will be set at the 0.05 level for a two-tailed test.

The repeated measures ANOVA will use all available data, using Maximum Likelihood methods as suggested by (<http://www.nap.edu/read/12955/chapter/1>).

Safety analysis will be performed in all subjects receiving at least one dose of the experimental drug. All AEs, SAEs and AEs leading to treatment discontinuation will be recorded, listed and compared in the two treatment arms at any follow-up visit and at the end of the study. The number of patients reporting at least one AE or SAE will be compared between the treatment arms using the fisher exact test. The total number of AE and SAE will be compared between the treatment arms using a poisson model. MedDRA code system will be used for all recorded AE/SAE.

Given the exploratory value of this study, multiple comparison adjustments for Type I errors will not be considered as a more conservative significance level would lead to miss any potential treatment effect. Furthermore, if there is a suggestive benefit ($p<0.1$) in the clinical measures and several of the biomarkers, this will be considered sufficient evidence for further study.

If at the end of the patient enrolment period less than 50% of patients are enrolled, an interim-analysis will be performed to decide whether or not to continue the trial.

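### AEs that limit treatment short of full discontinuation are counted as AEs but never identified as treatment-limiting, and it is unclear how a subject who stops one route is classified

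*Combined protocol and SAP*

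**What the plan says.** Protocol 2.2, objective 4, is "The tolerability and safety of RNS60 through the identification of unexpected adverse events". Two secondary endpoints bear on it. Item 6 of 2.4 is the number of subjects per arm "experiencing at least one AE leading to treatment discontinuation at 4, 12 and 24 weeks". Item 7 is "The mean number of AEs per treatment arm at 4, 12, 24 and 48 weeks".

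The safety paragraph of 11.2 uses matching categories: "All AEs, SAEs and AEs leading to treatment discontinuation will be recorded, listed and compared in the two treatment arms". It names a Fisher exact test for subjects with at least one AE or SAE and a Poisson model for event totals.

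Section 6.12 says that investigators "may reduce the dosage of study drug or discontinue the study drug in its entirety for AEs thought to be related to the study drug". It adds: "If the AE is mild or moderate, the dosage may be reduced until the event improves". The subject may then stay on the lower dose. On the two routes it says: "The option to continue with administration by IV only or inhalation only is allowable". Reasons and dates of every adjustment go into the CRF, and 9.3 has the action taken recorded for each AE.

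Section 11.3 says that two consecutive visits without an infusion, or less than half of the nebulized drug over three consecutive visits, imply withdrawal from the study.

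**The concern.** The regimen has two parts: a weekly infusion, and nebulization on the other six days. An AE can limit treatment in three ways: full stop, lower dose, or loss of one route. Only the first has a planned summary. An AE that led to a lower dose carries the same weight in item 7 as one that changed nothing.

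The arms could therefore look alike on item 6 while differing in how often AEs forced a reduction or ended one route. The all-AE comparisons would not separate such a difference from AEs of no consequence. A later trial would want to know which route is hard to tolerate, and the planned tables would not tell it.

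**Working it through.** **Step 1. Where each kind of AE goes under the current text.**

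| Response to the AE | Source | Item 6 | Item 7 and all-AE comparisons | Identified as treatment-limiting |
|---|---|---|---|---|
| Full stop because of the AE | 6.12 | Yes | Yes | Yes |
| Withdrawal: intolerable, drug-related, not remitting on down titration | 6.11 | Yes, if recorded as AE-led | Yes | Yes, if so recorded |
| Dose reduction, subject continues | 6.12 | No | Yes | No |
| One route stopped, other continues | 6.12 and 11.3 | Unclear | Yes | Unclear |

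**Step 2. The single-route subject.** Section 6.12 permits inhalation only or IV only. Under 11.3, an inhalation-only subject misses two consecutive infusions and an IV-only subject falls below half of the nebulized drug. Either meets a withdrawal criterion, and 11.3 makes no exception for the option in 6.12. The intake criterion in 6.11 does not say whether intake is judged per route or overall. If the subject is withdrawn, entry into item 6 depends on whether the recorded reason is the AE or non-compliance. If the subject continues, it depends on whether loss of one route counts as treatment discontinuation, which the available text does not define. Two analysts could reach different counts from the same data.

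**Step 3. Size.** The plan states no rate or power for item 6, so there is no figure to reproduce. Let f be the share of subjects with a treatment-limiting AE who are managed without discontinuation. The documents do not give f. It could lie anywhere from 0 to nearly 1.

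Illustration on assumptions: 71 per arm (6.7), two-sided 0.05 (11.2), Fisher test applied to item 6, and the same f in both arms. The rate seen by item 6 is the true rate × (1 − f). Power is the sum, over all pairs of counts with Fisher p ≤ 0.05, of the product of the two binomial probabilities.

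| Assumed true rates | f = 0 | f = 0.25 | f = 0.50 | f = 0.75 |
|---|---|---|---|---|
| 20% vs 5% | 73% | 55% | 31% | 7% |
| 10% vs 2% | 37% | 22% | 8% | about 1% |

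For the first row, the expected counts at f = 0 are 71 × 0.20 = 14.2 and 71 × 0.05 = 3.55. At f = 0.50 they are 7.1 and about 1.8. A count that also includes reductions and route stops returns to the f = 0 column.

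The wider count has limits of its own. At 10% versus 4% its power is 17%, and at 10% versus 5% it is 12%.

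**The case against.** The strongest reply is that little is lost. Every AE is counted in item 7 and compared in 11.2, whatever was done about it. Section 6.12 is permissive and equally allows a full stop. It requires one for serious or life-threatening events that are definitely drug-related, and 6.11 withdraws subjects whose intolerable drug-related AE does not remit. The worst intolerance therefore does reach discontinuation. The plan does not call item 6 the tolerability endpoint. Safety is secondary in this pilot, and the data for a by-route table are collected anyway. The public copy also omits 6.14 and the text of Section 7, which might hold definitions.

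All of this limits the point, but it does not close the gap: no planned analysis links an AE to a reduction or to the loss of one route. Collecting the fields is not the same as planning to report them. The conflict between 6.12 and 11.3 lies in text that is present.

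A reader might infer that most treatment-limiting toxicity would go uncounted. The documents do not support that: these AEs are counted, though not flagged, and no figure gives the share.

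A reader might also cite 1.4. The Phase I infusion study had no AE discontinuations, with headache in 55% (RNS60) and 33% (placebo). The first inhalation study had none, with oropharyngeal pain in 12.5%. These are AE rates, not rates of treatment-limiting AEs, and no dose reduction is described for them. They fit equally well with AEs that limited nothing.

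Finally, a reader might say that a subject who drops one route is scored as tolerating treatment. Because of 11.3, that is not settled either way.

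**Conclusion.** The point holds as a modest gap in reporting. Item 6 and 11.2 identify treatment-limiting AEs only through discontinuation, while 6.12 provides for other responses. An unknown share of tolerability problems, and the route behind them, would not be shown. The status of a single-route subject in item 6 is ambiguous. This rests on the text alone.

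The loss of power, from 73% to 31% at 20% versus 5% with half of the subjects missed, shows only that the gap could matter. The rates and f are assumptions, and if f is near zero almost nothing is lost. The primary biomarker analysis is not affected. This is a cheap improvement, not a flaw that threatens the trial.

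**What to change.** 1. Keep 2.4(6) and state whether treatment discontinuation means stopping either route or both.
2. Add to 2.4(6) and 11.2 the number of subjects per arm with at least one AE leading to discontinuation, dose reduction or stop of one route, at 4, 12 and 24 weeks. Show it by route and by type of action, and compare the arms with the Fisher test that 11.2 already names.
3. Reconcile 6.11, 6.12 and 11.3 on the single-route subject, so that status and recorded reason are unambiguous. Which rule applies is for the sponsor and investigators; no dosing or withdrawal rule is proposed here.

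The cost is a few lines of wording and one table. The data come from the adjustment record required by 6.12 and the action-taken field in 9.3. The downside is one more unadjusted exploratory safety comparison, with low power if the arms differ little, so the counts should be read mainly as description.
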